## 6.5 Screening, Enrollment, and Randomization

All patients who are clinically suitable for treatment with a DES and who meet the study inclusion criteria while not meeting any study exclusion criteria will be approached for inclusion in the study. Subjects who agree to participate will sign an Institutional Review Board (IRB) approved study informed consent and will proceed to the cardiac catheterization lab for further assessment of the angiographic inclusion and exclusion criteria.

If the subject meets all inclusion criteria and does not meet any of the exclusion criteria, randomization will be performed before planned use of rotational atherectomy, but after the guidewire has successfully passed the lesion and the subject will be considered enrolled in the study. Randomization will be an integrated functionality of the EDC.

If the subject fails to meet inclusion/exclusion criteria, s/he will be considered a screening failure and will be excluded from data collection. Treatment of screening failures will then proceed as would occur within the standard of care outside of the study.

## 6.6 Subject Termination or Withdrawal

Once enrolled, subjects may discontinue participation at any time by withdrawing informed consent or meeting the requirement for termination. Participation in the trial is entirely voluntary. Data from subjects who withdraw from the study will be included in all planned study analyses up until the point of withdrawal or exit. Any subject who is randomized and enters the study procedure but for whom the procedure is abandoned prior to attempted rotational atherectomy will be exited from the study.

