### 6.4.2 SECONDARY ENDPOINTS

- IVUS endpoints will be assessed at the following time points
  - Final IVUS (post Stent and post-dilatation)
    - In-segment Minimum lumen area ( $\text{mm}^2$ ), as assessed by IVUS after stent implantation and (optional) post-dilatation, referenced to the EEM
    - Minimum stent expansion (as defined as MSA  $\text{mm}^2$ ), as assessed by IVUS directly after stent implantation and post-dilatation
    - Mean stent expansion (%) –defined as mean stent area divided by the mean reference lumen area, where reference lumen area will be the average of the proximal and distal 10mm to the stent and/or the reference EEM at the site of MSA
    - Any dissection
    - Any malapposition
  - Pre-stent implantation post RA and CBA or POBA
    - Any dissection
    - Assessment of calcium fracture
- Angiographic endpoints measured in both in-stent, injured and in-segment (defined as injured or stent (whichever is larger) plus 5mm either end as feasible)

Page | 13

---

**CONFIDENTIAL AND PROPRIETARY:** This document and the information contained there-in may not be reproduced, used or disclosed without written permission from the Principal Investigators.

Version: 11\_dtd02Mar2023

IDE G210030

---

- Acute lumen gain (mm)
- Final residual diameter stenosis (%)
- Pre, pre-stent, and final minimum lumen diameter (mm)
- Pre-stent and final dissection type B or greater
- Final perforation (Ellis type  $\geq 2$ )
- Final side branch closure ( $\geq 1.5$ mm)
- Device-related endpoints as defined by any problems related to the devices, including but not limited to: balloon rupture, blade detachments, difficulty in withdrawing/advancing the device, or other device related problems as identified by the investigator.
- Clinical endpoints at 30-day and 270 day follow-up:
  - All-cause death (and further classified as cardiac and non-cardiac)
  - Myocardial infarction (as defined by the SCAI definition and Universal definitions, including peri-procedural myocardial infarction)
  - Target lesion revascularization
  - Target vessel revascularization
  - Stent thrombosis (definite/probable)
  - Major bleeding (BARC 3 or 5)
  - Vascular complications
  - Target Lesion Revascularization
  - Functional status (according to CCS class)

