## 8.4 Missed Follow-up

The Investigator(s) will make every attempt to follow the subjects. All subjects will be encouraged by the Investigator(s) to report any address or telephone number changes to the trial site. Subjects will be informed of the importance of completing the scheduled follow-up telephone calls even if they are not experiencing any medical issues. If a subject cannot be reached for a follow-up visit, or misses a scheduled visit, the visit will be recorded as a missed visit as of the date of last attempted contact. The procedure for attempts at contact should be three phone calls made and recorded in the study medical record plus mailing of a registered letter and contact with the General Practitioner, if allowed per patient consent.

Study subjects exit the trial when no additional follow-up visits, procedures, or data collection are required. A subject is exited from the trial in the following instances:

- Is lost-to-follow-up (LTFU)
- Voluntarily withdraws from the trial
- Death (Cause of death, if available, is to be reported)
- Completes last trial follow-up visit
- Investigator withdraws the subject from the trial

Once a subject has exited the trial, no further follow-up contact will be performed. However, if premature study exit has occurred, vital status may be obtained from public records if allowed by country law.

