## 9 ENDPOINT ANALYSIS AND STATISTICAL METHODS

### 9.1 Analysis Population

The analysis population is the 60 subjects who were enrolled and randomized to treatment with either rotational atherectomy or rotational atherectomy + cutting balloon atherotomy, regardless of procedure outcome. The analysis population excludes subjects who signed the informed consent but who failed to meet angiographic screening criteria (angiographic screen failures).

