### **9.3.2 Secondary Endpoint Testing**

Time-to-event analyses using Kaplan Meier methods will be performed for dichotomous clinical secondary endpoint outcomes, event rates in both groups will be compared using the log-rank test.

A 2-sided independent samples Student's t-test will be used with a 2-sided alpha of 0.05 to test for differences in continuous secondary endpoints between the control and experimental groups.

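### Section 6.6 exits randomized subjects whose procedure is abandoned before atherectomy, so later non-fatal outcomes go uncollected for subjects whom section 9.1 still counts

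*Combined protocol and SAP*

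**What the plan says.** Section 6.5 places randomization before atherectomy but "after the guidewire has successfully passed the lesion and the subject will be considered enrolled in the study". There is therefore an interval in which a randomized subject's procedure can stop before atherectomy is attempted. Section 6.6 provides for that case: "randomized and enters the study procedure but for whom the procedure is abandoned prior to attempted rotational atherectomy will be exited from the study". The same section keeps what was collected earlier: "Data from subjects who withdraw from the study will be included in all planned study analyses up until the point of withdrawal or exit".

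Section 8.4 sets the consequence of exit: "Once a subject has exited the trial, no further follow-up contact will be performed". Its one exception is optional and limited to survival, since "vital status may be obtained from public records if allowed by country law".

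Section 9.1 defines the analysis population as the 60 enrolled and randomized subjects, "regardless of procedure outcome". Only angiographic screen failures are left out. For the clinical endpoints, section 9.3.2 states: "Time-to-event analyses using Kaplan Meier methods will be performed for dichotomous clinical secondary endpoint outcomes", with a log-rank comparison. Section 6.4.2 lists those endpoints at 30 and 270 days, together with CCS class, and section 8.3 obtains the follow-up information by telephone.

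**The concern.** The plan counts these subjects in the analysis and also orders that their later non-fatal outcomes not be sought. Consent withdrawal and loss to follow-up are partly beyond the sponsor's control, but this loss is created by the protocol's own rule. An event such as a myocardial infarction, a revascularization or a major bleed after exit would not be ascertained, and neither would CCS class at either time point. An analysis plan of the kind cited in section 10.4 cannot recover data that were never collected.

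At stake is the completeness of the secondary clinical comparison by randomized arm. The primary endpoint is touched only under one reading of the word abandoned, which section 6.6 does not define.

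**Working it through.** **1. Does any other section restore follow-up?**

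| Section | What it covers | Captures a new non-fatal event after exit? |
|---|---|---|
| 8.4, list of exit reasons | Does not name an abandoned procedure, but 6.6 orders the exit and the no-contact sentence covers anyone who has exited | No |
| 8.5 | Asks for records of a revascularization, CABG or death; sets up no surveillance | No |
| 11.8 | Continues visits if the trial itself is terminated early | No |
| 12 | Monitors adverse events until participation is complete | No |
| 12.3 | Follows events already reported | No |

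The gap stands. It is limited to new non-fatal events and CCS class after exit. Data up to exit are kept, reported events are followed, and vital status may be obtained. Section 6.6 does not fix the moment of exit.

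**2. Size for a clinical endpoint.** The documents give neither an abandonment rate nor an event rate. Assumptions: 30 subjects per arm (60 subjects, 1:1, sections 6.1 and 9.2), *e* exits in one arm before any event, *k* observed events in that arm, and no other censoring.

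- Kaplan-Meier estimate = k/(30 − e)
- Bounds on the true proportion = k/30 to (k + e)/30
- Width of the undetermined range = e/30

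| e | Width (points) | k = 0 | k = 1 | k = 2 |
|---|---|---|---|---|
| 0 | 0 | 0.0% | 3.3% | 6.7% |
| 1 | 1/30 = 3.3 | 0.0% (0.0 to 3.3) | 1/29 = 3.4% (3.3 to 6.7) | 2/29 = 6.9% (6.7 to 10.0) |
| 2 | 2/30 = 6.7 | 0.0% (0.0 to 6.7) | 1/28 = 3.6% (3.3 to 10.0) | 2/28 = 7.1% (6.7 to 13.3) |

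Each cell gives the estimate, with the bounds in parentheses. An upper bound is reached only if every exited subject has the event. For comparison, the exact 95% interval for 2 of 30 with complete follow-up is 0.8% to 22.1%, a width of 21.3 points. One or two exits add 3.3 or 6.7 points of indeterminacy.

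**3. The primary endpoint, under each reading of abandoned.** If no stent is placed, there is no stent area and the exit removes nothing. If the subject is stented without atherectomy, a final-IVUS MSA could exist and could be lost, depending on when exit is deemed to occur.

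The second reading can be sized from the plan's own power table (section 9.2). The method is a two-sided two-sample t-test with SD 2.36 mm², alpha 0.05 and noncentrality δ/(2.36·√(1/n₁ + 1/n₂)). With 30 per arm it gives 0.733, 0.783, 0.828 and 0.866 for differences of 1.6, 1.7, 1.8 and 1.9 mm², which reproduces the table. At 1.8 mm²:

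- no MSA lost (30 and 30): noncentrality 2.954, power 0.828
- one lost (30 and 29): noncentrality 2.929, power 0.821
- two lost (30 and 28, or 29 and 29): power 0.814

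**The case against.** The strongest reply is about weight. The triggering interval is narrow: eligibility has been confirmed, the wire has crossed, and atherectomy was already planned (sections 6.3.1 and 6.5). The trial is a 60-patient pilot with no formal sample size calculation. Sections 6.6 and 9.1 can coexist: one says who is counted, the other says how long their data run, and censoring joins the two. All of this stands, and it is why the point is minor. It does not remove the point, because the censoring follows from a rule that could simply be dropped.

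A second reply is that keeping these subjects brings its own difficulty. If the lesion was never treated, a later first PCI of it could be counted as target lesion or target vessel revascularization, and stent thrombosis has no meaning without a stent. This is right, and the fix has to address it.

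Two stronger readings are tempting. A reader might infer that the rule biases the comparison between arms. The documents do not support that. The cutting balloon is used only after atherectomy (section 7.3.5), so bias would require abandonment to depend on the assigned arm. Nothing shows that it does. Nothing excludes it either, since blinding is described only for the final IVUS run (section 7.3.3) and the operator may know the allocation. A reader might also infer that all outcomes of these subjects are lost, or that they leave the analysis population. Sections 6.6, 8.4, 9.1 and 12.3 say otherwise.

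**Conclusion.** The point holds as an avoidable gap in the secondary clinical data. Sections 6.6 and 8.4 together stop the collection of new non-fatal events and of CCS class for subjects whom section 9.1 retains, and no other section repairs this.

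The size is probably small. On the assumption of 30 per arm and exit before any event, each exit leaves up to 3.3 points of that arm's event proportion undetermined, well inside the sampling error of the estimate. The number of exits is unknown and may be zero.

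It should not be said without qualification that the primary endpoint is untouched, or that it is damaged. That turns on whether abandonment includes stenting without atherectomy, which section 6.6 leaves open. Even then, one or two lost values lower power at 1.8 mm² by about 0.7 or 1.4 percentage points. The sections should be reconciled, as a minor and inexpensive improvement.

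**What to change.** Replace the last sentence of section 6.6 with wording to this effect:

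> If the procedure stops after randomization but before atherectomy is attempted, the subject stays in the randomized population, completes the 30- and 270-day telephone contacts unless consent is withdrawn, and is analysed in the assigned arm. Any MSA obtained from a final IVUS run is kept in the primary analysis.

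State in section 6.6 whether an abandoned procedure includes one in which a stent is placed without atherectomy. In section 9.3.2, state how target lesion revascularization, target vessel revascularization and stent thrombosis are counted when the lesion was left untreated; for example, a later first PCI of that lesion could be reported separately. A line in section 8.4 that an abandoned procedure alone is not a reason for exit would help, but the operative change is in section 6.6.

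The cost is a protocol amendment, with the associated FDA and IRB review, and two telephone calls per affected subject within the existing schedule. The statistical price is that a few retained subjects who did not receive the assigned strategy would dilute the treatment contrast. The change concerns follow-up and analysis only and alters no treatment.

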## 7 STUDY PROCEDURES

### 7.1 Subject Screening and Informed Consent

All subjects who are clinically suitable for PCI treatment with rotational atherectomy and a DES and meet study eligibility requirements will be asked to participate in further screening and will be asked to sign a study-specific IRB approved study consent form prior to angiography.

### 7.2 Schedule of assessments

Assessment	Inclusion and Baseline	Procedure	Discharge	30 Days (+/-7 d) (Telephone contact)	270 Days (± 21 d) (Telephone contact)
Demographic characteristics	X				
Medical History, cardiac history, and risk factors	X				
Angina status	X		X	X	X
Physical examination 	X				
NYHA class	X				
CCS class	X		X	X	X
Laboratory Assessments 	X		X 		
12-lead electrocardiogram	X		X		
Previous medications	X				
Clinical inclusion/exclusion criteria	X				
Informed Consent	X				
Pregnancy test (if applicable)	X				
Angiography		X			

Page | 15

**CONFIDENTIAL AND PROPRIETARY:** This document and the information contained there-in may not be reproduced, used or disclosed without written permission from the Principal Investigators.

Version: 11\_dtd02Mar2023

IDE G210030

Effective Date: 3/23/2023

End Date: 2/14/2024

Pre-procedural IVUS (if feasible)		X			
Inclusion/exclusion criteria		X			
Randomization		X			
Atherectomy +/- CBA		X			
Post-lesion preparation IVUS		X			
Stenting procedure		X			
Postprocedural blinded IVUS		X			
Antiplatelet/antithrombotic medication		X	X	X	X
Adverse Event Assessment		X	X	X	X
Medication changes 		X	X	X	X

Physical examination: height and weight (at inclusion only), heart rate and blood pressure. CBA – Cutting balloon atherectomy

Hematology and blood chemistry, creatinine, and low-density lipoprotein cholesterol

[figure not shown]
Changes to cardiovascular medications collected only.

In acute patients CK and/or CK-MB or troponin prior to the procedure and in the case of signs/symptoms of myocardial infarction/myocardial ischemia. Laboratory assessments including CK and/or CK-MB or Troponin should be done prior to procedure and at discharge in patients presenting with signs/symptoms of acute coronary syndrome/myocardial infarction/myocardial ischemia. \*Patients with STEMI are excluded from the trial (see exclusion criteria 4).

## 7.3 Procedure overview

### 7.3.1 Study flow chart

### 7.3.2 Coronary Angiography

Coronary angiography for off-line QCA analysis will be performed 1) at baseline, 2) after each step of the lesion preparation, and 3) at the end of the procedure. After intracoronary injection of 100-200mcg of nitroglycerine, coronary angiography will be performed in two orthogonal projections aimed to minimize lesion foreshortening and differing at least 30° of rotation. The catheter tip, filled with dye, should be visible for QCA calibration and the lesion should ideally be located in the center of the field of view.

### 7.3.3 Intravascular Ultrasound Assessment

Intravascular ultrasound assessment for off-line analysis will be performed with the following strategy. The 60Mhz OptiCross™ IVUS catheter (Boston Scientific, Marlborough, MA, USA) using automated pull-back at 1mm/s. The catheter will be advanced at least 5 mm distal to the target lesion.

- 1) at baseline, prior to any intervention, if possible. This IVUS run is optional
- 2) after lesion preparation defined as RA + POBA or RA + CBA, and
- 3) at the end of the procedure. This will be following completion of the interventional procedures per the interventional cardiology investigator.

During the procedure, any additional IVUS runs and assessments deemed clinically indicated by the treating physician to guide the procedure will not be precluded from being performed; these will occur prior to the Final post-angioplasty IVUS run.

Only after the operator deems the procedure to be finished, will the final post angioplasty IVUS run be performed for endpoint assessment. In order to reduce bias, operators will be blinded to the final IVUS run pullback images and no additional stent placement or post dilation is allowed after the Final IVUS run. Blinding will be performed by either turning the IVUS console results away from the primary investigator in the room, or having the primary investigator turn away, if the former is not feasible.

To ensure safety, an unblinded physician will be available at the end of the procedure to review the results of the Final IVUS run for safety signals not present on fluoroscopy. If the unblinded physician has any safety-related concerns, the operator will take immediate actions to ensure the safety of the patient.

### 7.3.4 Rotational Atherectomy (RA) Strategy

Rotational atherectomy will be performed according to the instructions for use and current best practices using a maximum burr-to-artery ratio of 0.4-0.6, a burr speed of 140,000 – 160,000 RPM, and a maximum run duration of 20s. Burr upsizing during the procedure is allowed but the maximum burr-to-artery ratio is not to exceed the recommended 0.6.

Page | 18

**CONFIDENTIAL AND PROPRIETARY:** This document and the information contained there-in may not be reproduced, used or disclosed without written permission from the Principal Investigators.

Version: 11\_dtd02Mar2023

IDE G210030

Effective Date: 3/23/2023

End Date: 2/14/2024

### **7.3.5 Cutting Balloon Atherectomy (CBA) Strategy**

In patients randomized to RA+CBA, cutting balloon atherectomy using a Wolverine™ cutting balloon (Boston Scientific, Marlborough, MA, USA) will be performed after rotational atherectomy. The Wolverine cutting balloon will be sized 1:1 relative to the reference vessel diameter and the inflation pressure is recommended at 6 ATM and is expected not to exceed the device rated burst pressure of 12 ATM.

### **7.3.6 Procedure Strategy**

The following procedure strategies should be followed in regard to overall treatment strategy of the study subject:

- Additional lesions may be treated during the same procedure or may be staged according to the discretion of the operator
- Study subjects are to be maintained on dual antiplatelet therapy or oral anticoagulation with single or dual antiplatelet therapy according to applicable guidelines

## **8 FOLLOW-UP ASSESSMENTS**

### **8.1 Post-procedure Management**

Standard of care hospital protocols for the management of patients after treatment with DES shall be followed.

### **8.2 Discharge Assessment**

All subjects shall be discharged from the hospital at the discretion of the attending clinical team. Per the standard of care, and at some time prior to dismissal, all subjects shall undergo an assessment of angina status, a 12-lead ECG, and the following lab assessments: hematology and blood chemistry, CK-MB or troponin I, and creatinine. Subjects who had acute angina prior to the procedure, or experienced any events between the procedure and discharge, will have CK and/or CK-MB or troponin I repeated upon discharge. Changes to cardiovascular medications will be collected at discharge as well as an assessment of adverse events.

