## 11.8 Stopping Rules

A stopping rule based on the occurrence of clinically relevant coronary dissection was defined on the basis of literature review. In previous pilot studies evaluating a strategy of rotational atherectomy with or without cutting balloon, the meta-analytic incidence of coronary dissection was 18% (2-sided 95% upper confidence limit = 28%).(13, 14) Therefore, a stopping rule is set at the occurrence of 11 (18% of 60 patients) flow-limiting coronary dissections leading to a periprocedural myocardial infarction.(17) That is, if during

Page | 25

**CONFIDENTIAL AND PROPRIETARY:** This document and the information contained there-in may not be reproduced, used or disclosed without written permission from the Principal Investigators.

Version: 11\_dtd02Mar2023

IDE G210030

Effective Date: 3/23/2023

End Date: 2/14/2024

the enrollment phase, 11 episodes of flow-limiting coronary dissection associated with periprocedural myocardial infarction occur, patient recruitment will be terminated.

If the trial is terminated prematurely or suspended, the sponsor shall promptly inform the clinical investigators and regulatory authorities of the termination or suspension and the reason(s) for this. The investigator shall then promptly inform the reviewing IRB. The sponsor will, as soon as possible, provide a written statement to the investigators to enable prompt notification of the IRBs. If the trial is terminated early, follow-up visits will continue for all enrolled subjects for the intended length of the study.

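### Periprocedural MI rests on a post-procedure marker with no stated draw time and, in stable subjects, no required pre-procedure value

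*Combined protocol and SAP*

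**What the plan says.** **Routine sample (Section 8.2).** The timing is "at some time prior to dismissal, all subjects shall undergo an assessment of angina status, a 12-lead ECG, and the following lab assessments", and the laboratory list is "hematology and blood chemistry, CK-MB or troponin I, and creatinine". No hours after the procedure are given. The end of the interval is set locally: "All subjects shall be discharged from the hospital at the discretion of the attending clinical team".

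**Repeat sample (Section 8.2).** Two groups have the marker repeated at discharge. One is subjects with acute angina before the procedure. The other is those who "experienced any events between the procedure and discharge, will have CK and/or CK-MB or troponin I repeated upon discharge".

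**Baseline (Section 7.2).** Footnote 2 defines the laboratory panel as "Hematology and blood chemistry, creatinine, and low-density lipoprotein cholesterol", with no cardiac marker. Footnote 4 asks for a pre-procedure marker only in acute patients or those presenting with signs or symptoms of ACS, MI or ischemia. Section 6.1 describes the 60 patients as having stable CAD.

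**Use of the result.** Section 6.4.2 lists MI as a secondary endpoint, "including peri-procedural myocardial infarction". Section 11.8 ends recruitment if 11 episodes of "flow-limiting coronary dissection associated with periprocedural myocardial infarction occur".

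**Adjudication and follow-up.** Section 12.6 blinds the clinical events committee to treatment. The 30- and 270-day contacts are by telephone, with no laboratory tests (Sections 7.2 and 8.3).

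**The concern.** A marker-based diagnosis of periprocedural MI depends on when blood is drawn and on the level before the procedure. The plan fixes the first for nobody and requires the second only in acute or symptomatic patients. Two stable subjects with the same injury could be recorded differently because one was sampled while the marker was still rising. A stable subject with a chronically raised level could look like a case.

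Sampling intensity also differs between subjects. One trigger for the repeat arises after randomization, so a subject with an in-hospital event has a second chance of a positive result.

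At stake are the interpretability of the MI endpoint, which Section 9.3.2 compares between arms by log-rank test, and one component of the event counted by the only stopping rule. The primary endpoint, IVUS minimum stent area, is not affected.

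**Working it through.** **1. The passages side by side, for a stable subject without an in-hospital event**

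| Item | Required? | Source |
|---|---|---|
| Pre-procedure marker | No | 7.2, footnotes 2 and 4 |
| Post-procedure marker | Yes under 8.2; footnote 4 ties discharge markers to symptomatic patients | 8.2; 7.2, footnote 4 |
| Time after procedure | Not stated | 8.2 |
| Draw time recorded | Not requested in any section | 7.2, 8.2, 13.8 |
| Repeat marker | No | 8.2 |
| Later laboratory test | None scheduled | 7.2, 8.3 |

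Even on the wider reading (Section 8.2), this subject has one value at an unknown time and nothing to subtract from it. Reconciling 8.2 with footnote 4 would settle who is sampled after the procedure. It would settle neither the timing nor the baseline.

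**2. The plan's own figure.** The stopping threshold reproduces: 0.18 × 60 = 10.8, rounded up to 11. The concern changes no stated figure.

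**3. How far draw time could matter (illustration only).** Nothing in this step is in the documents. Assume that the marker follows f(t) = (t/tp)·exp(1 − t/tp), where tp is the time of peak; that peaks are log-normal with log SD σ; and that 10% of subjects exceed the MI cut-off at peak. The share of true cases detected at time t is P(Z > 1.2816 − ln f/σ)/0.10.

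| Draw | f, tp = 12 / 18 / 24 h | Detected, σ = 1.0 | Detected, σ = 1.5 |
|---|---|---|---|
| 3 h | 0.53 / 0.38 / 0.30 | 28 / 13 / 6% | 44 / 27 / 19% |
| 6 h | 0.82 / 0.65 / 0.53 | 70 / 43 / 28% | 79 / 58 / 44% |
| 12 h | 1.00 / 0.93 / 0.82 | 100 / 88 / 70% | 100 / 92 / 79% |

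One worked entry: tp = 24, t = 6 gives f = 0.25 × exp(0.75) = 0.53 and ln f = −0.636. With σ = 1.0, P(Z > 1.918)/0.10 = 0.28. The numbers depend on the model. The direction does not: while a marker is still rising, an earlier draw detects fewer cases.

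**4. In events.** A 10% true rate gives 0.10 × 30 = 3 cases per arm. If one arm were sampled at 6 h and the other at 12 h, the recorded difference would be 3 × (1.00 − 0.79) = 0.6 events at the low end (tp = 12, σ = 1.5) and 3 × (0.879 − 0.433) = 1.3 at the high end (tp = 18, σ = 1.0). The documents give no reason to expect such a gap between arms. Without one, both arms lose sensitivity alike.

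**5. Stopping rule (illustration only).** Detection rates of 80% and 60% are assumed. The true rates are the 18% and 28% that Section 11.8 gives for coronary dissection, used here as if they were rates of the narrower stopping event. Then P(at least 11 of 60) is:

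| True rate | Full detection | 80% | 60% |
|---|---|---|---|
| 18% | 0.53 | 0.24 | 0.05 |
| 28% | 0.97 | 0.82 | 0.43 |

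This shows what missed MIs would do to the rule, not that they will be missed.

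**The case against.** **Standard of care and the committee charter.** Section 8.2 places the discharge tests within standard care, and Section 8.1 invokes hospital protocols, which may set a draw time. The CEC Charter holds definitions and process. Neither is in the documents, and local practice may differ between the two sites. Blinded adjudication limits classification bias but cannot supply a missing baseline. ECGs at baseline and discharge mean that MI evidence is not marker-only, but they do not make a single marker value interpretable.

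**An arm-aware discharge team.** A reader might infer that staff who know the arm control the result through discharge timing. The text does not support this. Operators must know which device they used and are blinded only to the final IVUS run, but no passage says whether the discharging team knows the arm. Discharge only closes the interval for the routine sample; it fixes the time of the repeat alone. The repeat also has a baseline trigger, acute angina, which is unrelated to arm.

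**A stopping count that runs low.** This too is tempting, but a subject with a flow-limiting dissection has plausibly had an event that triggers the repeat. The point is not fully settled, since a dissection during the procedure is not clearly an event after it. An undercount is possible, not shown.

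**Scale.** This is a 60-patient pilot with an imaging primary endpoint and no power claim for MI. That stands, and it limits the weight of the point.

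**Conclusion.** The concern holds as a defect of ascertainment. As written, the plan fixes no time for the post-procedure marker and requires no pre-procedure value in stable subjects, so a raised value in such a subject cannot be told from a chronic elevation. If the Section 6.1 description holds, this applies to most or all of the 60. Entry criteria exclude primary PCI for STEMI but not every acute presentation, so the exact share is unknown.

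Recorded periprocedural MI can vary with draw time and with the event-triggered repeat. A spurious treatment difference of any particular size is not established. The 1.3- to 2.5-fold ratios that the model in the working would give for 6 h against 12 h need a between-arm timing gap that the documents do not describe. The size and direction of any between-arm effect are unknown. The reason to act is that the omission cannot be repaired after the procedure and costs little to prevent.

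**What to change.** In Sections 7.2 and 8.2, edited together with the reconciliation of footnote 4 and Section 8.2:

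1. Add the chosen marker to the baseline blood draw for all subjects.
2. State one post-procedure sampling time or narrow window, identical in both arms and chosen by the sponsor. A wide window would not do: in the illustrative model with tp = 24 h and σ = 1.0, detection runs from 28% at 6 h to 100% at 24 h.
3. Record the date and time of every draw on the eCRF, and flag samples taken outside the window.
4. Give the events committee both the baseline and the post-procedure values.
5. Keep event-triggered repeats in the endpoint and in the stopping count, identified as such. Add a sensitivity analysis limited to scheduled samples. Dropping the repeats could remove real MIs.

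The cost is one added assay per subject on blood already being drawn, an eCRF time field and protocol wording. Some subjects who leave before the window opens will have a value flagged as early. No treatment or discharge decision needs to change.
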